5.3 EXCLUSION CRITERIA

1. Threshold blood pressure of 80/40 mmHg-- patients with both a systolic blood pressure of less than 80 mmHg and a diastolic blood pressure of less than 40 mmHg.
2. Irreversible brain damage based on available historical and clinical information.
3. Patients with a solid organ transplant or those with a bone marrow or stem cell transplant in the previous 100 days or who have not engrafted.
4. Acute or chronic use of circulatory support device, other than ECMO, such as LVADs, RVADs, BIVADs.
5. Presence of preexisting advanced chronic renal failure (i.e., ESRD) requiring chronic renal replacement therapy prior to this episode of acute kidney injury or with pre-existing chronic kidney disease (CKD) defined as a eGFR <30 ml/min/1.73m 2 . Patients who have never seen a pediatric nephrologist will be assumed not to have pre-existing CKD.
6. AKI occurring in the setting of burns, obstructive uropathy, vasculitis, scleroderma renal crisis, atheroembolism, functional or surgical nephrectomy, cyclosporine or tacrolimus nephrotoxicity.
7. Received >12 hour of CRRT (not including SCUF on ECMO) during this hospital admission or prior to transfer from an outside hospital.
8. Received >1 hemodialysis treatment during this hospital admission or prior to transfer from an outside hospital.
9. Metastatic malignancy which is actively being treated or may be treated by chemotherapy or radiation during the subsequent three month period after study therapy.
10. Chronic immunosuppression with the exception of corticosteroids up to a dose of 10 mg per day.
11. HIV or AIDS.
12. Severe chronic liver failure as determined by standard diagnostic requirements.

13. Current Do not Attempt Resuscitation (DNAR), Allow Natural Death (AND), or withdrawal of care status, or anticipated change in status within the next 7 days.
14. Patient not expected to survive 28 days because of an irreversible medical condition. (This is not restrictive to AKI, and may include situations such as the presence of irreversible brain damage, untreatable malignancy, inoperable life threatening condition, or any condition to which therapy is regarded as futile by the PI.)
15. Any medical condition that the Investigator thinks may interfere with the study objectives.
16. Physician refusal.
17. Dry weight <15 kg.
18. Platelet count <15,000/mm³.

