6.2.3 SCD PLACEMENT IN CRRT / ECMO CIRCUIT

Appendix M illustrates the integration of the CRRT circuit and SCD into the ECMO circuit. The CRRT return will be post pump.

Patients who receive CRRT on ECMO almost always develop their AKI, and hence their need for CRRT, after they have been on ECMO for at least 24 hours. Thus, the additional extracorporeal volume (ECV) associated with the CRRT circuit is not a factor, as the blood volume from ECMO is stable. In fact, the contribution of

the CRRT circuit is decreased (in terms of percent of ECV) since the ECMO circuit adds to the patient blood volume.

The pressure gradients are not an issue with CRRT on ECMO. In the most standard configurations, the CRRT circuit draws blood from the ECMO circuit post-pump and returns blood to the ECMO circuit pre-membrane, which is the safest configuration. The CRRT circuit will therefore see positive pressure from the ECMO circuit, and the current CRRT machines are designed to handle this. The CRRT pumps however, regulate the pressures within the CRRT circuit, so the SCD will see similar pressures compared to a non-ECMO situation.

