6.3 BASELINE PERIOD

The Baseline Period begins at enrollment and ends at the start of the Observation Period. It is expected that the patient will begin the Observation Period before the patient has reached 12 hours of CRRT. The following information will be recorded as close to the start of the Observation Period as possible. Data from standard of care tests may be used as baseline data, as long as it is captured within the time frames noted.

- **Demographic Data**
 - a) Date of birth
 - b) Gender
 - c) Race/ethnicity
- **Hospitalization Data**
 - a) Hospital Admission Date
 - b) Hospital Admission Diagnosis
 - c) ICU Admission Date
 - d) ICU Admission Diagnosis
 - e) Medical History
- **Vital Signs/Physical Assessment (within 12 hours prior to the start of Observation Period unless otherwise indicated)**
 - Temperature
 - Blood Pressure, heart rate,
 - Body weight (within 24 hours if available)
 - PRISM II Score
 - Physical Exam
 - Urine Output (previous 24 hours)
 - ICU percent fluid overload at CRRT initiation (Defined as [(Fluid In (liters) – Fluid Out (liters))/ICU admission weight (kg)] x 100% where Fluid In and Fluid Out are calculated from ICU admission to CRRT initiation.
- **Clinical Laboratory Tests (within 12 hours prior to the start of Observation Period)**
 - CBC with differential
 - BUN/Creatinine
 - Na, K, Cl, HCO₃, Ca, Mg, Ionized Ca, PO₄
 - ALT, AST, Bilirubin, ALP, Total Protein, Albumin, Glucose
 - PT, PTT, INR
 - Urinalysis (if urine available)
- **Respiratory**
 - Status – Ventilator support (yes/no; date of intubation)
 - If on Vent: FiO₂
 - If on Vent with an arterial line: Arterial Blood Gas (12 hours prior to start of Observation Period)
 - If on Vent without an arterial line: Arterial Blood Gas (if available within 12 hours of start of Observation Period)
- **Blood for Research**
 - Blood sample will be sent to an outside laboratory for testing of biomarkers
- **Other (Event-driven)**
 - Acknowledgement (yes/no) to critical medications administered to the patient in the 24 hours prior to start of Observation Period
 - Adverse Events occurring since enrollment
 - Microbiology/culture data (within the last 72 hr.)

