7. TREATMENT INTERRUPTIONS – DISCONTINUATION CRITERIA

7.1. TREATMENT INTERRUPTION CRITERIA

The SCD is to be used continuously along with CRRT and changed every 24 hours and at any time the circuit exhibits significant clotting that impairs the functionality of the circuit.

In the event that a procedure is needed (e.g. CT-Scan, MRI), SCD treatment may be interrupted for a maximum of 12 hours (cumulative) per 24 hour period for these indications. In the event a patient needs to initiate ECMO in the middle of the SCD course, SCD treatment may be interrupted for up to 24 consecutive hours. Cumulative interruption of greater than 12 hours (or 24 hours for ECMO) will trigger the end of Observation Period and immediate initiation of the Follow-up period. These patients will not be removed from the study unless consent is withdrawn.

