Besides the test of the hypothesis the study is focused on observable, empirical and laboratory determinations of patient safety while on the SCD. Previous human trials have been conducted on the SCD device and the protocol contains a review of AE and SAE data from all SCD human studies and findings from those studies contributed to constructing the investigative safety profile. Safety endpoint measures specified in the protocol include adverse events, laboratory safety parameters, vital signs, ventilation status and hemodynamic variables. Device integrity and performance measurements are also defined as are circumstances which demand premature termination of SCD treatment.

Prolonged exposure to the SCD is anticipated to result in superior outcomes, although as noted above, this pilot study is not designed to assess for efficacy. However, we understand that a minimum amount of exposure to the SCD will be required for an appropriate safety analysis and for making any inference regarding efficacy. The ppCRRT experience demonstrated that the majority of patients (201/370) received CRRT for 1 to 7 days and exhibited 65% survival (Symons et al CJASN 2007 Table7). Assuming our trial includes patients with similar illness severity, we have established a 72 minimum number of hours a patient will be treated with the SCD to be included in the final outcome analysis.

This trial is an early safety efficacy study but is not powered for statistical significance. Insights into a comparison of historical controls matched to SCD treated patients will utilize the ppCRRT Registry to match for: etiology of AKI, co-morbidities, CRRT modality, dose and form of anticoagulant, adverse events. [10].

The ppCRRT Registry has data fields for the primary reason for CRRT, including AKI and its cause, as well as co-morbidities which will be matched for primary organ system involvement. The CRRT modality was evenly distributed between convective and diffusive modality, with 60% of the convective modalities provided as CVVH and 40% as CVVHDF. The anticoagulant protocol will be standardized with ACD-A/CaCl₂ and all centers used the same protocol in ppCRRT Registry as outlined in this study protocol. Thus, the ppCRRT Registry dataset will be able to be matched to our study patient cohort. Also as noted above, patients will be matched for age, size and PRISM II score.

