The Prospective Pediatric CRRT (ppCRRT) database will be used as a control for the CRRT treatment related factors including: patient age, gender, primary cause of AKI, total treatment duration, CRRT modality (CVVH, CVVHD, CVVHDF), CRRT small solute clearance (ml/1.73m²/hour), baseline estimated GFR (using the original Schwartz formula, which was used in the ppCRRT), urine output in the 24 hours prior to CRRT initiation (ml/kg/hour), percent fluid overload at CRRT initiation based on admission ICU weight, vasoactive medication number at time of CRRT initiation and mean airway pressure at CRRT initiation.

An additional analysis will also evaluate patients who have achieved targeted iCa levels during 90% of treatment time and those who do not.

In summary this protocol meets all criteria necessary for clinical scientific inquiry related to a test of hypothesis in a well monitored environment focused on patient safety during the conduct of the study. Basic statistics will be performed on the data sets along with historical data comparisons and subjected to subset analysis where appropriate. The results will help to guide the design of a future pivotal study of this device.

The rational for therapy, study objectives and endpoints, design, inclusion and exclusion criteria are explicitly defined. Patient safety parameters are well documented including safety reporting, safety observations and assays, procedures for patient withdrawal and study discontinuation criteria along with monitoring device integrity and performance. Lastly, a review of all prior SCD human study safety data is included in the protocol for full disclosure to study investigators and the informed consent document includes a full description of all known and potential risks of the device treatment.

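### ECMO patients may enrol, but ECMO is not a registry matching or control factor and has no dedicated baseline item, so an ECMO patient can be paired with a non-ECMO control

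*Combined protocol and SAP*

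**What the plan says.** **ECMO is allowed.** Exclusion 4 in Section 5.3 bars "Acute or chronic use of circulatory support device, other than ECMO, such as LVADs, RVADs, BIVADs". Exclusion 7 bars patients who have "Received >12 hour of CRRT (not including SCUF on ECMO) during this hospital admission", so slow ultrafiltration on ECMO does not count towards the limit. Section 6.2.3 describes the ECMO circuit and states: "Patients who receive CRRT on ECMO almost always develop their AKI, and hence their need for CRRT, after they have been on ECMO". The time on ECMO that it gives is 24 hours or more. Section 7.1 provides for starting ECMO during treatment ("In the event a patient needs to initiate ECMO in the middle of the SCD course") with its own interruption allowance, which Appendix E repeats.

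**The registry comparison.** Section 11 gives the factors in three places. The first is to "match for: etiology of AKI, co-morbidities, CRRT modality, dose and form of anticoagulant, adverse events", with co-morbidities matched by primary organ system. The second says "patients will be matched for age, size and PRISM II score". The third lists control factors: age, gender, cause of AKI, treatment duration, CRRT modality, small solute clearance, baseline GFR, urine output, percent fluid overload, and finally "vasoactive medication number at time of CRRT initiation and mean airway pressure at CRRT initiation". ECMO is in none of them.

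**Baseline data.** Section 6.3 asks for PRISM II within the 12 hours before the Observation Period, and for percent fluid overload, "where Fluid In and Fluid Out are calculated from ICU admission to CRRT initiation". Neither Section 6.3 nor Appendix F has an item for ECMO status.

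**The concern.** A matched historical comparison balances only what it matches on, or what those factors stand in for. ECMO is a major support treatment that the eligibility criteria permit, and the plan has no ECMO match, stratum, exclusion or sensitivity analysis. The listed severity measures would usually be taken while ECMO is running, so they cannot be assumed to stand in for it.

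The comparison of mortality and dialysis dependency with historical data is a stated objective (Synopsis and Section 3.1). It is also part of the Synopsis evaluation plan and a planned DSMB evaluation (Section 10). Section 11 says the results will help to guide a pivotal design. If the ECMO share differs between trial patients and their controls, the observed difference mixes that imbalance with any device effect. If ECMO status is not captured in structured form, this cannot be reliably examined afterwards.

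**Working it through.** The plan states no sample-size, power or alpha figure to reproduce. The check sets passages side by side and then gives an illustration of scale.

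**Step 1. Can an ECMO patient enrol?** Yes: exclusions 4 and 7, Sections 6.2.3 and 7.1, and Appendix E.

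**Step 2. Does any listed factor identify ECMO?** No. The nearest is co-morbidity by primary organ system, and patients with the same organ system involved may or may not be on ECMO.

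**Step 3. When are the severity factors recorded?**
- ECMO has usually run for at least 24 hours when CRRT starts (Section 6.2.3).
- The Observation Period starts with CRRT or within its first 12 hours (Section 6.4), so the PRISM II window opens at most 12 hours before CRRT. ECMO would then usually have run for at least 24 − 12 = 12 hours.
- Vasoactive number is taken at CRRT initiation, so usually on ECMO.
- The fluid-overload window runs from ICU admission to CRRT initiation. It can include time on ECMO and fluid removed by the exempt ultrafiltration.
- Appendix A scores blood gases and blood pressure in PRISM II and has no rule for ECMO.

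That these values may fail to separate ECMO from non-ECMO risk is an inference from timing and definitions. The documents do not state it.

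**Step 4. Scale, on assumed figures.** Bias in the mortality difference = f × g, where f is the share of trial patients on ECMO but paired with non-ECMO controls, and g is the mortality gap left after the other matching. Neither is in the documents. N = 16 comes from Section 10, which places the historical-control efficacy evaluation there.

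| Mismatched of 16 | f | g = 10 points | g = 20 points | g = 30 points |
|---|---|---|---|---|
| 2 | 0.125 | 1.3 | 2.5 | 3.8 |
| 4 | 0.25 | 2.5 | 5.0 | 7.5 |
| 8 | 0.50 | 5.0 | 10.0 | 15.0 |

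With 4 mismatched, the shift equals 0.025 × 16 = 0.4 to 0.075 × 16 = 1.2 deaths. At the enrolment cap of 30, 4 mismatched patients (f = 0.133) give 1.3 to 4.0 points.

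**Step 5. Sampling error.** Section 11 quotes 65% survival in registry patients treated for 1 to 7 days, so reference mortality is 35%. Ignoring pairing, the standard error of a 1:1 difference is √(2 × 0.35 × 0.65 / N):
- N = 16: √(0.455 / 16) = 16.9 points
- N = 30: √(0.455 / 30) = 12.3 points

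Every shift in the table is below one standard error at N = 16. Unlike sampling error, the bias would not shrink with more patients.

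**The case against.** **The comparison is secondary in weight.** Section 11 says the study is not designed to assess efficacy and is not powered. This stands and limits the consequence, but a descriptive comparison can still be biased.

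**The plan may already cover ECMO in part.** The control-factor list is worded as open-ended, Section 11 allows unspecified subset analyses, and Appendix F records procedures at baseline and throughout. Applying the separate ECMO interruption allowance also requires ECMO starts to be known. The case report form is not in the documents and may hold more. All true, but none of this commits the plan to recording ECMO status at CRRT initiation or to matching on it.

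**Distortion is not demonstrated.** A reader might infer that ECMO improves the listed measures, so that an ECMO-dependent child is matched to a less ill one. The documents do not show this. In Appendix A the blood-gas and pressure items carry at most 3 + 5 + 6 + 6 = 20 of 75 points. Section 6.2.3 says the ECMO circuit adds to patient blood volume, so the direction for fluid overload is unsettled. Mean airway pressure is a weak example: it is a Section 11 control factor but is not in the trial data listed in Sections 6.3 and 6.4 or Appendix F. What stands is narrower: these factors cannot be relied on to stand in for ECMO.

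**Another exact-match factor costs pairs.** About 16 factors are already named for perhaps 16 patients, and Section 11 also requires 72 hours of SCD treatment for the final outcome analysis. This stands and is counted in the fix.

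**Conclusion.** The gap is real: ECMO patients are admitted by design, ECMO is in no matching or control list, and no ECMO-specific analysis is planned. As written, an ECMO patient can be paired with a non-ECMO control.

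Its size cannot be fixed from the documents. With 4 of 16 mismatched and a residual gap of 10 to 30 points, both assumed, the shift is 2.5 to 7.5 points against a standard error of about 17 points.

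Three stronger readings are not supported:
- That the gap could make the SCD look effective. If ECMO mortality is higher and the excess ECMO patients are on the trial side, the bias runs against the SCD.
- That the bias is large. This would need a high ECMO share, no ECMO among the matched controls and a crude rather than residual mortality gap. The documents establish none of these, and do not say that the registry lacks ECMO patients.
- That ECMO is the largest treatment difference the criteria permit. The documents offer nothing by which to rank such differences.

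This is a cheap improvement to make before the matching is done, not a defect that undermines the safety objective.

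**What to change.** 1. Add to the baseline data a yes/no item for ECMO at CRRT initiation, and record any later ECMO start with its date.
2. Add ECMO at CRRT initiation to the Section 11 matching factors, matched exactly where the registry holds the field.
3. Pre-specify a sensitivity analysis of the registry comparison restricted to non-ECMO trial patients. If the registry lacks ECMO status, make this the main registry comparison, describe ECMO patients separately, and state as a limitation that the controls may include ECMO patients.
4. Keep safety analyses on all patients.

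The cost is one baseline field, one event record and a few sentences in Section 11. The downside is that some matched pairs may be lost from an already small cohort, even if the registry records ECMO.

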Duration of Subject Participation	Each patient will be followed for 60 days following enrollment.
Inclusion Criteria	
 1. A patient, or legal representative, has signed a written informed consent form. 2. Must be receiving medical care in an intensive care unit (e.g., PICU, MICU, SICU, CTICU, Trauma). 3. Age less than 22 years. 4. Females of child bearing potential who are not pregnant (confirmed by a negative serum pregnancy test) and not lactating if recently post-partum. 5. Intent to deliver full supportive care through aggressive management utilizing all available therapies for a minimum of 96 hours. 6. Clinical diagnosis of AKI due to etiologies requiring CRRT (see Appendix B). AKI is defined as acute kidney injury with any one of the following: 
 • Increase in SCr by ≥ 0.3 mg/dL (≥ 26.5 $\mu\text{mol/L}$) within 48 hours or; • Increase in SCr to ≥ 1.5 times baseline, which is known or presumed to have occurred within the prior 7 days or; • Urine volume $<0.5\text{ml/kg/h}$ for 6 hours 7. At least one non-renal organ failure (defined as receiving mechanical ventilation or at least one vasoactive medication to treat hypotension) OR presence (proven or suspected) of sepsis. (Appendix C).

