6.4 STUDY OBSERVATION PERIOD

The Study Observation Period begins when the patient starts treatment and will continue up to a maximum of 168 hours from the time of Observation Start. **Patient will begin the Observation Period before the patient has reached 12 hours on CRRT.** A patient may begin CRRT therapy and SCD treatment at the same time, which would also mark the beginning of the Study Observation Period.

This observation period has been broken into seven 24 hour time periods. It ends when the patient has reached 168 hours in the observation period or when the patient meets the termination criteria outlined in **Section 7.2** as determined by the Principal Investigator or Medical Team at the participating Clinical Site.

All tests are scheduled on a 24 hour cycle, or once a day, and can be scheduled to be drawn around each participating site's ICU blood drawing schedule, with the exception of any test that requires a specific draw frequency.

The following information will be obtained for patients enrolled during the study observation period on a daily basis unless otherwise specified:

- **Vital Signs/Physical Assessment**
 - Temperature
 - Blood Pressure , heart rate
 - Urine Output (previous 24 hours)
 - Net Fluid Balance (previous 24 hours)
- **Clinical Laboratory Tests**
 - CBC with differential – every 12 hours (+/- 4 hours)
 - BUN, Creatinine
 - Na, K, Cl, HCO₃, Ca, ionized Ca, Mg, PO₄
 - ALT, AST, Bilirubin, ALP, Total Protein, Albumin, Glucose
 - PT, PTT, INR
- **Respiratory**
 - Status – Ventilator support (yes/no; date of extubation)
 - If on Vent: FiO₂
 - If on Vent with an arterial line: Arterial Blood Gas
 - If on Vent without an arterial line: Arterial Blood Gas (if available)
- **Blood for Research**
 - Collect at hours 48, 96, 144, and end of study (+/- 4 hours). If study observation period ends prior to hour 168, collect at end of study observation period. Blood for biomarkers will be collected as close as possible to the time of SCD scheduled changes in the days required (+/- 4 hours) if practical.
 - Blood sample will be sent to an outside laboratory for testing of biomarkers

- **CRRT Parameters (Start at hour 0)**
 - Parameters include modality, blood flow rate, net fluid removal, dialysate or replacement solution flow rate, citrate infusion rate, calcium replacement rate.
 - System performance (circuit survival - event driven)
 - Post filter ionized calcium (+/- 1 hour)

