6.5.2 DAY 28 POST ENROLLMENT

This visit may be done via telephone call or office visit. Please record the following information on day 28 (+7 days) following enrollment:

- Presence / date of mechanical ventilation (since last visit)
- Presence / date of renal replacement therapy (since last visit)
- Serious Adverse events (since last visit)
- Serum creatinine (if an office visit takes place)

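### Registry controls have no stated time zero and no survival landmark, although trial patients can enter after up to 12 hours of CRRT

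*Combined protocol and SAP*

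**What the plan says.** **Entry.** Exclusion 7 in Section 5.3 rules out a patient who has "Received >12 hour of CRRT (not including SCUF on ECMO) during this hospital admission or prior to transfer from an outside hospital", so shorter prior CRRT is allowed. Section 6.4 adds: "Patient will begin the Observation Period before the patient has reached 12 hours on CRRT". It also allows a zero gap: "A patient may begin CRRT therapy and SCD treatment at the same time". Section 6.1 places consent and a sponsor eligibility check before enrolment.

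**Trial clock.** The synopsis states: "Each patient will be followed for 60 days following enrollment". Section 6.5.2 does the same for the earlier visit: "Please record the following information on day 28 (+7 days) following enrollment". Section 6.5.3 repeats this for day 60. Enrolment is not the start of SCD, because Section 6.3 says: "The Baseline Period begins at enrollment and ends at the start of the Observation Period".

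**Controls.** Section 11 takes controls from the ppCRRT registry and lists the factors to be controlled. Several are fixed at CRRT initiation, including "vasoactive medication number at time of CRRT initiation and mean airway pressure at CRRT initiation". One, total treatment duration, is known only later. Section 11 also limits the final outcome analysis to patients with at least 72 hours of SCD and states no equivalent for controls. No section gives the moment from which a control's mortality is counted.

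**The concern.** A child who dies on CRRT before consent, sponsor validation and enrolment are complete never becomes a trial patient. A registry child who dies at the same point in the illness can still be a control unless a rule prevents it. If that happens, the trial side is selected for survival to entry and the control side is not, so SCD mortality looks lower even if the device does nothing.

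In-hospital mortality, which Section 3.2 names among the efficacy measures, is exposed in the same way. It has no day count, so it depends on which deaths are in the control pool.

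The bias does not shrink as patients are added. Section 10 plans an efficacy comparison with historical controls, and Section 11 says the results will inform a pivotal design. An avoidable tilt towards the device is worth removing.

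**Working it through.** The plan gives no power, alpha, margin or control rate for this comparison, so there is no design figure to reproduce.

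**1. Time origins side by side**

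| | Trial patient | Registry control |
|---|---|---|
| Covariates fixed at | baseline, some at CRRT initiation (such as "ICU percent fluid overload at CRRT initiation") | CRRT initiation |
| CRRT time already survived at time zero | 0 to 12 hours | not stated |
| Day-28 and day-60 clock | from enrolment | not stated |

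Appendix D adds to the ambiguity. In defining duration of renal support it treats the start of renal replacement therapy as the start of the observation period. These are different moments for anyone with earlier CRRT.

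**2. Size if controls are counted from CRRT initiation**

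Inputs:
- m, total control mortality, set at 50%. This is the general figure for critically ill patients with AKI in the synopsis rationale, not a registry rate.
- e, the share of controls who die before the matched entry time. The documents give no value. I assume 2% to 5% for a full 12-hour gap.

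Mortality among controls who could have entered = (m − e)/(1 − e). Bias = m − (m − e)/(1 − e).

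- e = 2%: (0.50 − 0.02)/(1 − 0.02) = 0.48/0.98 = 49.0%; bias 1.0 point.
- e = 5%: (0.50 − 0.05)/(1 − 0.05) = 0.45/0.95 = 47.4%; bias 2.6 points.
- e = 0 (enrolled at or before CRRT start): bias 0.

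For each assumed e these are upper limits, because they give every patient the full 12-hour gap. They also count deaths only. Requiring controls to be still on CRRT would remove some who stopped early because they improved, which pulls the other way.

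**3. In numbers of patients**

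- 16 patients: expected deaths fall from 8.0 to 7.84 (e = 2%) or 7.58 (e = 5%), a shift of about 0.2 to 0.4 of a death.
- 30 patients: from 15.0 to 14.69 or 14.21, a shift of about 0.3 to 0.8.
- For scale, the exact 95% interval for 8 deaths in 16 is 25% to 75%.

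**4. Effect on a test**

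The protocol names no test. As an illustration, take a one-sided exact binomial test of 16 patients against a fixed 50%, rejecting at 4 or fewer deaths. Its false-positive rate is 3.8% without the bias, 4.6% with e = 2% and 6.0% with e = 5%.

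**The case against.** **Control time zero is only an inference.** A reader might conclude that controls are followed from CRRT initiation. The documents do not say so; they say when certain covariates are measured. This objection stands, so the bias is conditional. What is established is that the origin is unstated and no landmark exists.

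**Total treatment duration is a listed factor.** Matched closely, especially against patients with at least 72 hours of SCD, it would exclude most controls who died within 12 hours. This stands in part. No caliper or algorithm is given, duration is one of many factors, and it is partly a result of the clinical course. It may reduce the problem but cannot replace a landmark.

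**The gap is not 12 hours for everyone.** A reader might infer that every trial patient has survived 12 hours of CRRT. CRRT and SCD may start together, and the bias is then zero.

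**The interval up to SCD start is not free of deaths.** A reader might suppose that it is. A death between enrolment and SCD start is a trial death under the enrolment clock. Only the 72-hour restriction would remove it.

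**The registry survival figure is not a valid base.** It is tempting to use 35% mortality, from the 65% survival in Section 11. That figure belongs to the 201 of 370 patients who had CRRT for 1 to 7 days. The stratum already leaves out CRRT of under a day, so subtracting 12-hour deaths from it would remove deaths it never contained.

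**The comparison is not powered.** Section 11 says so, and the shift is under one death in 16 or in 30 patients. This limits the priority of the point but does not remove the bias.

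**Conclusion.** The point holds as a missing alignment rule with a predictable direction. Entry can follow up to 12 hours of CRRT, trial outcomes are counted from enrolment, and nothing requires a control to have reached the same elapsed CRRT time alive and on treatment. If control mortality runs from CRRT initiation, early control deaths favour SCD.

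The size cannot be known from the documents. With 50% total mortality and an assumed 2% to 5% of controls dying within 12 hours, it is at most about 1.0 to 2.6 points, and zero for patients enrolled at or before CRRT start. That is small beside the sampling error of 16 to 30 patients.

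A reader might also infer that control day 60 falls materially earlier in the illness than trial day 60. The shift is at most about 12 hours, against a visit window of +7 days, and is not worth pursuing. The rule should be added because it is cheap and because larger numbers would not remove the bias.

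**What to change.** Add to Section 11, in substance:

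> *For a patient enrolled t hours after CRRT initiation (t = 0 if enrolled at or before CRRT start), eligible controls are registry patients alive and still on CRRT at t hours. Days 28 and 60 are counted from enrolment in the patient and from t in the control. If registry times are not recorded by hour, a common landmark (12 hours or day 1, as the registry allows) is applied to both groups as a sensitivity analysis. Any analysis restricted to 72 hours of SCD applies the corresponding landmark to controls.*

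The patient's clock should stay at enrolment. Moving it to SCD start would conflict with the enrolment-based endpoints and drop enrolled patients who die before SCD. The common landmark also drops any trial patient who dies between enrolment and the landmark, so it belongs in a sensitivity analysis.

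Record CRRT start, enrolment and SCD start times on the case report form. Section 6.3 does not list CRRT start time as a baseline item, although sites need it to apply exclusion 7.

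Cost: one matching rule, three time stamps and a somewhat smaller control pool.
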